# 5.5.1.2. Dose Modifications and Dose Reductions

Dose-limiting toxicity (DLT) is defined as any one of the following events:

- Grade 4 hematologic toxicity for > 1 day
- Grade 3 hematologic toxicity with complications (e.g., thrombocytopenia with bleeding)
- Failure of Grade 3 thrombocytopenia, absolute neutrophil count (ANC), hemoglobin to recover to Grade ≤ 1 within 4 weeks despite the use of platelet and red blood cell (RBC) transfusions and/or growth factors
- ≥ Grade 3 non-hematologic toxicity not due to disease progression (excluding Grade 3 nausea, vomiting or diarrhea that is adequately controlled with supportive care and resolves to ≤ Grade 2 within 48 hours, or Grade 3 electrolyte disturbances responsive to correction within 24 hours)
- $\geq$  Grade 3 liver function tests (LFTs) lasting > 72 hours
- Treatment interruption > 14 days due to toxicity
- Other important medical event

Subjects who require a dose reduction due to toxicity will be considered to have had a DLT.

No DLTs were experienced in the Monotherapy Safety Run-in Phase and no dose reductions were required for toxicity. If a DLT is experienced in  $\geq 2$  of 6 subjects in the Combination Safety Run-in Phase during Cycle 1, no further subjects will be enrolled at that dose level. Subjects who experience a DLT may continue treatment at the next lower dose level until disease progression or

Confidential 33
December 31, 2019 Protocol Amendment 4

unacceptable toxicity. The MTD is defined as the doses of E6201 plus dabrafenib at which  $\leq$  1 of 6 subjects experiences a DLT.

Subjects who experience E6201- and/or dabrafenib-related toxicity requiring a dose reduction may continue treatment at the next lower dose level for either drug until disease progression or unacceptable toxicity. Adverse events considered for dose reduction should not include the events assessed by the investigator as exclusively related to underlying disease or other medical condition or concomitant treatment. If treatment must be delayed for reasons other than toxicity, contact the Medical Monitor to discuss the reasons for delay and plans for resuming study therapy.

The E6201 dose modification guidelines are outlined in Table 4. Provisions are not made for dose levels below 160 mg/m² twice weekly. If 160 mg/m² twice weekly is determined to be unsuitable based on toxicity as defined above, the subject will be permanently discontinued from E6201 treatment.

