**Table 4: E6201 Dose Modification Guidelines** 

E6201-Related Toxicity a	During a Cycle	Dose Adjustment for Next Treatment Day
Grade 1		
	Continue treatment	Maintain dose level
Grade 2		
First incidence	Interrupt until resolved to Grade 0-1 or baseline	Maintain dose level
Second incidence	Interrupt until resolved to Grade 0-1 or baseline	240 mg/m  twice weekly (75% of dose)
Third incidence despite dose reduction	Interrupt until resolved to Grade 0-1 or baseline	160 mg/m² twice weekly (50% of dose)
Fourth incidence despite dose reduction	Discontinue treatment permanently	NA
Grade 3		
First incidence	Interrupt until resolved to Grade 0-1 or baseline	240 mg/m² twice weekly (75% of dose)
Second incidence	Interrupt until resolved to Grade 0-1 or baseline	160 mg/m² twice weekly (50% of dose)
Third incidence despite dose reduction	Discontinue treatment permanently	NA
Grade 4		
First incidence b	Interrupt until resolved to Grade 0-1 or baseline	160 mg/m² twice weekly (50% of dose)
Second incidence despite dose reduction	Discontinue treatment permanently	NA

NA = not applicable.

- a: Excluding Grade 3 nausea and vomiting not controlled by antiemetics, insomnia, obesity/weight gain, infertility, amenorrhea, galactorrhea, glucose intolerance due to dexamethasone used as an antiemetic, asymptomatic hypercholesterolemia or hypertriglyceridemia, and any  $\geq$  Grade 3 nonhematological toxicities due to disease and disease progression.
- b: Grade 4 toxicities judged to be E6201-related and considered life-threatening require discontinuation of study treatment. E6201 treatment following non-life-threatening Grade 4 toxicities could resume following discussion with sponsor.

E6201 Dose modifications for QTc prolongation are defined in Table 5 below.

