Other Adverse Reactions c , including Hemorrhage	

 
Intolerable Grade 2
 
Any Grade 3
 
	
 
Withhold TAFINLAR.
 
If improved to Grade 0-1, resume TAFINLAR at lower dose.
 
If not improved, permanently discontinue TAFINLAR.
 

First occurrence of any Grade 4	
 
Withhold TAFINLAR until improves to Grade 0-1, then resume at a lower dose.
 
Or
 
Permanently discontinue TAFINLAR.
 

 
Recurrent Grade 4
 
	Permanently discontinue TAFINLAR.

 
aNational Cancer Institute Common Terminology Crit
 
4.0.
 
bSee Table 6 for recommended dose reductions of TA
 
	·

<sup>cDose modification of TAFINLAR is not required for new primary cutaneous malignancies.

Confidential 37
December 31, 2019 Protocol Amendment 4

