#### 5.5.1.3. Schedule Adjustments for Toxicity

• Dosing delays are permitted for either E6201 or dabrafenib. Once a toxicity has resolved to ≤ Grade 1, the subject may resume treatment. The dose level must be reduced to the next lower dose level when treatment is re- initiated following a delay for drug-related toxicity unless otherwise specified.

• The maximum delay allowed between treatment cycles for either E6201 or dabrafenib is 2 weeks. If toxicity has not resolved after 2 weeks of delay, the Medical Monitor should be contacted to discuss permission for resuming treatment after a longer delay for subjects who are experiencing clinical benefit.

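### For E6201-related events, the dose-reduction sentence cancels the two Grade 3 exclusions in the DLT definition, and Table 4 footnote a exempts the wrong nausea and vomiting

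*Combined protocol and SAP*

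**What the plan says.** Section 5.5.1.2 lists the events that count as dose-limiting; the Synopsis and Section 5.1 carry the same list. The bullet on Grade 3 or higher non-hematologic toxicity has two carve-outs:

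- gastrointestinal events: "excluding Grade 3 nausea, vomiting or diarrhea that is adequately controlled with supportive care", provided they fall to Grade 2 or lower within 48 hours;
- electrolytes: "Grade 3 electrolyte disturbances responsive to correction within 24 hours".

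The sentence after the list adds a second route to a DLT, with no exception: "Subjects who require a dose reduction due to toxicity will be considered to have had a DLT".

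Three rules decide when a reduction is required.

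- **Table 4 (E6201).** A first related Grade 3 event means interruption, then 240 mg/m², which is 75% of the starting 320 mg/m². The column is headed "Dose Adjustment for Next Treatment Day". Footnote a gives the exceptions and begins "Excluding Grade 3 nausea and vomiting not controlled by antiemetics". It does not mention controlled nausea or vomiting, diarrhea, or electrolyte events.
- **Table 7 (dabrafenib).** This is recommended label guidance. For any other Grade 3 reaction dabrafenib is withheld, and then "If improved to Grade 0-1, resume TAFINLAR at lower dose".
- **Section 5.5.1.3.** "Dosing delays are permitted for either E6201 or dabrafenib", but restarting after a delay for drug-related toxicity requires a step down unless another rule says otherwise.

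The DLT count drives the dose. Two or more DLTs among six subjects in Cycle 1 closes the level, and the MTD is the level with at most one in six. The Expansion Phase is treated at that MTD.

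**The concern.** One part of the definition says that certain Grade 3 events are not dose-limiting. For the same events, when related to E6201, Table 4 requires a reduction and the next sentence turns that reduction into a DLT. No text says which part prevails, so a site and the Safety Review Committee could classify identical data differently.

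Footnote a makes this harder to resolve. A footnote meant to agree with the DLT list would spare the controlled events. This one spares the uncontrolled ones, so by Table 4 the milder event lowers the dose and the worse one does not.

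At stake is the dose carried into the Expansion Phase, where the intracranial response rate is measured. A level could be closed because of events that the list says should not close it.

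The event types are plausible for this drug. In Part B of the earlier solid-tumor study (Section 3.1.4), treatment-related nausea was reported in 8 of 30 subjects, vomiting in 5 of 30 and hypokalemia in 4 of 30. These are any-grade figures and say nothing direct about Grade 3. Section 5.5.2 permits prophylaxis for nausea, vomiting and diarrhea only after Cycle 1, although treatment of these symptoms is allowed during Cycle 1.

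**Working it through.** The plan gives no operating characteristics for the DLT rule, so there is no figure to reproduce. The check is a trace of the rules, followed by an illustration of size.

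**Step 1. Trace each Grade 3 event in Cycle 1 at 320 mg/m².**

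| Event | DLT list | Table 4 with footnote a | After the reduction sentence |
|---|---|---|---|
| E6201-related nausea or vomiting, controlled, Grade 2 or lower in 48 h | Not a DLT | Reduce to 240 mg/m² | DLT |
| E6201-related diarrhea, same course | Not a DLT | Reduce to 240 mg/m² | DLT |
| E6201-related electrolyte event, corrected in 24 h | Not a DLT | Reduce to 240 mg/m² | DLT |
| E6201-related nausea or vomiting, not controlled | DLT | Exempt from reduction | DLT (by the list) |
| Any of the first three, unrelated to either drug | Not a DLT | Does not apply | Not a DLT |

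The first three rows are the contradiction and the fourth is the reversed footnote. The fifth shows that the exclusions keep a function: the list bullet has no drug-relatedness test, so without them an unrelated event of this kind would be a DLT.

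E6201 is given on Days 1, 4, 8, 11, 15 and 18. A reduction at the next treatment day can therefore fall inside Cycle 1.

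**Step 2. Worked case.** Two of six subjects at Dose Level 1 have controlled E6201-related Grade 3 vomiting in Cycle 1, and nobody has another listed DLT.

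- By the list: 0 of 6, so the level qualifies as the MTD.
- By the reduction sentence: 2 of 6, so the level closes and the next level uses 240 mg/m². Since 240/320 = 0.75, that is 25% less E6201.

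**Step 3. How often the two counts would disagree.** Let L be the probability that a subject has a listed DLT, and a the added probability of having only an excluded event that forces a reduction. Both are assumptions, because the documents give neither. For six subjects,

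P(p) = 1 − (1 − p)^6 − 6p(1 − p)^5

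Every listed DLT is in both counts, so the probability of disagreement is P(L + a) − P(L).

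- P(0.05) = 0.0328, P(0.06) = 0.0459, P(0.08) = 0.0773
- P(0.10) = 0.1143, P(0.11) = 0.1345, P(0.13) = 0.1776

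| | a = 1% | a = 3% |
|---|---|---|
| L = 5% | 0.0132 | 0.0445 |
| L = 10% | 0.0202 | 0.0633 |

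Differences were taken before rounding. At a = 1% the counts disagree in about 1% to 2% of cohorts.

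**Step 4. What the documents suggest about a.** For E6201 alone, Section 3.1.4 names abdominal pain, hyperbilirubinemia, QT prolongation, syncope and dyspnea as the most common Grade 3/4 events. Section 3.4.1 names neutropenia, thrombocytopenia and fatigue as the related Grade 3/4 events on the twice-weekly schedule. Neither names nausea, vomiting, diarrhea or an electrolyte event, though the first gives only the most common terms. The four monotherapy subjects in this trial had one related event, a Grade 2 thrombocytopenia. Chemistry is scheduled only on Day 1 of each cycle (Section 5.1), so short electrolyte events may go unseen in Cycle 1. Nothing is given for the combination.

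**The case against.** The strongest reply is that the rules can be read together. The exclusions sit inside one bullet and narrow only that bullet; a required reduction is a separate route. List or reduction is then one usable rule, and it errs toward caution in a first combination cohort. This is a fair reading and may be what was intended. But then the exclusions do nothing for E6201-related events, and footnote a is still reversed.

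Four stronger readings are tempting, and the documents do not support them.

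- **That the exclusions are void altogether.** They still apply to events unrelated to study drug, which Sections 5.5 and 5.5.1.2 keep out of dose reduction.
- **That uncontrolled nausea and vomiting go unmanaged.** They remain listed DLTs, and a subject with a DLT may continue at the next lower level. The footnote removes only Table 4's reduction schedule.
- **That Table 7 should be changed too.** It also lowers dabrafenib after any Grade 3 reaction, but it reproduces label guidance. Departing from it in Cycle 1 is a debatable safety trade-off, not the correction of an error.
- **That the trigger of at least 1 of 3 in the dose-level table enlarges the effect.** It would, but it conflicts with the MTD rule of at most 1 of 6 whatever happens to these exclusions, so it is a separate matter.

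Oversight is a partial mitigation: the Safety Review Committee reviews run-in data before expansion, and safety is reviewed monthly. Neither tells a site which count to use.

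**Conclusion.** The point holds for E6201-related events. The list excludes them, Table 4 reduces the dose for them, and the next sentence counts the reduction. Footnote a is reversed whichever count was intended. This rests on the text alone.

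The practical size is uncertain and probably small: about 1% to 2% of six-subject cohorts under the rule of at least 2 of 6, if excluded events occur in 1% of subjects and listed DLTs in 5% to 10%. A reader might infer much more by assuming excluded events in 5% or 10% of subjects, which gives disagreement of 8.1% to 10.9% or 19.1% to 23.0%. The Grade 3/4 data for E6201 alone give no support for rates that high. Dabrafenib could add events, but no figure is given.

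Severity is minor to should-fix: the effect is probably rare, but it acts on the rule that sets the expansion dose and is cheap to remove.

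**What to change.** 1. In Table 4 footnote a, replace the exemption for nausea and vomiting that antiemetics do not control with the DLT list's own two exclusions. For these events, hold E6201 until Grade 0-1 or baseline, then resume at the same dose.
2. In Section 5.5.1.3, cite the footnote as a case where another rule applies, so that restarting E6201 after such an event does not require a step down.
3. Keep the sentence that a required reduction is a DLT wherever it appears (Synopsis, Sections 5.1 and 5.5.1.2), but limit it to reductions required in Cycle 1 for the MTD count.
4. Leave Table 7 unchanged. A required dabrafenib reduction still counts as a DLT, and the list should say so.

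If the sponsor intends the broad count, the list should say that the exclusions do not apply to drug-related events, and footnote a should still be corrected.

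The cost is wording edits, with no added subjects or procedures. The downside is a slightly less conservative DLT count for these E6201 events and a return to the same E6201 dose after them. An event attributed to dabrafenib as well would still count if it required a dabrafenib reduction.

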**Table 4: E6201 Dose Modification Guidelines** 

E6201-Related Toxicity a	During a Cycle	Dose Adjustment for Next Treatment Day
Grade 1		
	Continue treatment	Maintain dose level
Grade 2		
First incidence	Interrupt until resolved to Grade 0-1 or baseline	Maintain dose level
Second incidence	Interrupt until resolved to Grade 0-1 or baseline	240 mg/m  twice weekly (75% of dose)
Third incidence despite dose reduction	Interrupt until resolved to Grade 0-1 or baseline	160 mg/m² twice weekly (50% of dose)
Fourth incidence despite dose reduction	Discontinue treatment permanently	NA
Grade 3		
First incidence	Interrupt until resolved to Grade 0-1 or baseline	240 mg/m² twice weekly (75% of dose)
Second incidence	Interrupt until resolved to Grade 0-1 or baseline	160 mg/m² twice weekly (50% of dose)
Third incidence despite dose reduction	Discontinue treatment permanently	NA
Grade 4		
First incidence b	Interrupt until resolved to Grade 0-1 or baseline	160 mg/m² twice weekly (50% of dose)
Second incidence despite dose reduction	Discontinue treatment permanently	NA

NA = not applicable.

- a: Excluding Grade 3 nausea and vomiting not controlled by antiemetics, insomnia, obesity/weight gain, infertility, amenorrhea, galactorrhea, glucose intolerance due to dexamethasone used as an antiemetic, asymptomatic hypercholesterolemia or hypertriglyceridemia, and any  $\geq$  Grade 3 nonhematological toxicities due to disease and disease progression.
- b: Grade 4 toxicities judged to be E6201-related and considered life-threatening require discontinuation of study treatment. E6201 treatment following non-life-threatening Grade 4 toxicities could resume following discussion with sponsor.

E6201 Dose modifications for QTc prolongation are defined in Table 5 below.

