## 5. INVESTIGATIONAL PLAN

# 5.1. Overall Study Design

This is a Phase 1 study of E6201 for the treatment of CNS metastases in BRAF V600-mutated metastatic melanoma. A total of N = 28 - 34 subjects with melanoma metastasized to the CNS will be included.

Selected subjects will be: both males and females age  $\geq 18$  years; histologically confirmed melanoma with BRAF V600 mutation with CNS metastasis; archived tumor sample from the primary, recurrent or metastatic disease with documented BRAF mutation; no prior treatment with BRAF or MEK inhibitors for systemic disease; recovered from all acute toxicities ( $\geq$  Grade 1) due to prior immunotherapy; determined to have adequate renal and hepatic function, and no known history of significant cardiac disease.

Monotherapy Safety Run-in Phase: Following screening, a total of 4 subjects were enrolled. E6201 was administered by intravenous (IV) infusion over a 2-hour period at a dose of 320 mg/m^2 twice weekly (Days 1, 4, 8, 11, 15 and 18) for 3 weeks, repeated every 28 days (1 cycle), until progression of disease, observation of unacceptable adverse events, intercurrent illness or changes in the subject's condition that prevented further study participation.

Combination Safety-Run-in Phase: Following screening, a total of 6 - 12 subjects are anticipated to establish the recommended doses of E6201 plus dabrafenib. E6201 will be administered by IV infusion over a 2-hour period twice weekly (Days 1, 4, 8, 11, 15 and 18) repeated every 28 days plus dabrafenib orally twice daily (=1 cycle), according to the schedule below.

Dose Level	E6201 (IV)	Dabrafenib (PO)
1	320 mg/m² (MTD monotherapy)	150 mg BID (market dose)
-1ª	240 mg/m² (Dose Level -1)	150 mg BID
-2ª	240 mg/m² (Dose Level -1)	100 mg BID (Dose Level -1)
-3ª	160 mg/m² (Dose Level -2)	100 mg BID (Dose Level -1)
-4 a	160 mg/m² (Dose Level -2)	75 mg BID (Dose Level -2)
-5 a	160 mg/m² (Dose Level -2)	50 mg BID (Dose Level -3)

<sup>a If necessary based on DLT ( $\geq 1$  of 3 or  $\geq 2$  of 6 subjects experience DLT at the previous dose level)

Subjects who demonstrate clinical benefit (objective response or stable disease) will be allowed to continue therapy with E6201 plus dabrafenib until progression of disease, observation of unacceptable adverse events, intercurrent illness or changes in the subject's condition that prevents further study participation.

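### Table 4's fixed E6201 resume doses suit only a 320 mg/m² start; for subjects assigned 240 mg/m², two of its five dose-change rows give no reduction

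*Combined protocol and SAP*

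**What the plan says.** Section 5.1 starts the combination run-in at E6201 320 mg/m² (level 1). Below it are two levels at 240 mg/m² (-1 and -2) and three at 160 mg/m² (-3 to -5). The footnote to that table allows a step down when at least 1 of 3 or at least 2 of 6 "subjects experience DLT at the previous dose level". Expansion then treats up to 18 subjects at the resulting combined MTD, with run-in subjects treated at the MTD counted towards that number. Dose reductions apply in Expansion too.

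Section 5.5.1.2 says subjects with drug-related toxicity "requiring a dose reduction may continue treatment at the next lower dose level for either drug until disease progression or unacceptable toxicity". It also says: "Subjects who experience a DLT may continue treatment at the next lower dose level until disease progression or" unacceptable toxicity. It makes no provision below 160 mg/m²: if that dose "is determined to be unsuitable based on toxicity as defined above, the subject will be permanently discontinued from E6201 treatment". For E6201 dose modifications it refers the reader to Table 4.

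Table 4 has five rows that set a new dose. The second Grade 2 and first Grade 3 rows print 240 mg/m² "twice weekly (75% of dose"). The third Grade 2, second Grade 3 and first Grade 4 rows print 160 mg/m², labelled as 50%. The third Grade 2 row is headed "Third incidence despite dose reduction".

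Section 5.5.1.3 says the dose "must be reduced to the next lower dose level when treatment is re- initiated following a delay for drug-related toxicity unless otherwise specified".

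**The concern.** The printed doses were evidently written for subjects starting at 320. For a subject assigned 240, the second Grade 2 and first Grade 3 rows return the subject to 240, so nothing is reduced. The table then contradicts itself, because the third Grade 2 row presumes a reduction that never happened. For a subject assigned 160, the same two rows print a higher dose than the one that caused the toxicity.

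The text around the table points to the next lower level. But Section 5.5.1.2 sends the reader to the table, and the rule in 5.5.1.3 yields where something else is specified. A site can therefore take the table as the exception and re-treat at an unchanged dose.

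DLT counting is also affected, because Section 5.5.1.2 states: "Subjects who require a dose reduction due to toxicity will be considered to have had a DLT". The same Cycle 1 event could count as a DLT under one reading and not under the other, and the MTD depends on that count. The practical scope is mainly events that are not DLTs in their own right: a second Grade 2 event, or an uncomplicated Grade 3 hematologic event. Most Grade 3 non-hematologic events are already DLTs. Scheduled Cycle 1 hematology is on Day 1 only (Appendix D), so a mid-cycle hematologic event would be found only by an unscheduled test.

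**Working it through.** **Inputs.** E6201 levels 320, 240 and 160 mg/m² (Section 5.1); resume doses 240 and 160 (Table 4); six doses per cycle; anticipated combination run-in of 6 to 12 subjects, with 6 at the MTD (Section 5.1); 0 DLTs in 4 monotherapy subjects at 320 (Section 3.4.1).

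**1. The plan's own labels.** 240/320 = 75% and 160/320 = 50%. Both reproduce, but only from 320.

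**2. Change in dose by row**, (printed dose − assigned dose)/assigned dose:

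| Table 4 row | Printed dose | From 320 | From 240 | From 160 |
|---|---|---|---|---|
| Second Grade 2 | 240 | −25% | 0% | +50% |
| Third Grade 2 | 160 | −50% | −33% | 0% |
| First Grade 3 | 240 | −25% | 0% | +50% |
| Second Grade 3 | 160 | −50% | −33% | 0% |
| First Grade 4 | 160 | −50% | −33% | 0% |

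Measured against the assigned dose, a 320 start gives five reductions, a 240 start three, and a 160 start none.

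**3. Using the percentages instead does not help.** From 240, 75% is 180 mg/m², which is not a defined level, and 50% is 120, below the 160 floor. From 160 they give 120 and 80, both below the floor.

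**4. Exposure.** 6 × 240 = 1440 mg/m² per cycle against 6 × 160 = 960. The difference is 480, and 480/960 = 50% more.

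**5. Is a 240 start within the planned run-in?** Run-in size = (subjects per failed level × number of failed levels) + 6.

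| MTD level | 3 per failed level | 6 per failed level |
|---|---|---|
| −1 (240) | 9 | 12 |
| −2 (240) | 12 | 18 |
| −3 (160) | 15 | 24 |

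Level −1 fits within 6 to 12 either way. Level −2 fits only with 3 per failed level. Level −3, the first at 160, does not fit in either case.

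**6. How likely is a step down from 320?** The documents give no DLT rate for the combination, so the true Cycle 1 rate p is assumed.

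- Rule A, 2 or more of 6 alone: 1 − P(X ≤ 1 | n = 6, p).
- Rule B, 1 or more of the first 3 also closes the level: 1 − (1 − p)³ × P(X ≤ 1 | n = 3, p).

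| p | Rule A | Rule B |
|---|---|---|
| 0.10 | 0.114 | 0.291 |
| 0.20 | 0.345 | 0.541 |
| 0.30 | 0.580 | 0.731 |

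The first step down is always to 240. The monotherapy result of 0 in 4 has a Clopper-Pearson 95% upper limit of 1 − 0.025^(1/4) = 0.602, and it concerns E6201 alone.

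**The case against.** The strongest reply is that, read as a whole, the protocol already sends a 240 subject to 160. The exception in 5.5.1.3 has a natural referent in Table 4's first Grade 2 row, which interrupts treatment and then keeps the dose. The 240 rows are plainly meant as reductions. Section 5.3 states 320 mg/m² for both combination phases, which explains how the table came to be written. On this view the table is unclear, not an instruction to skip a reduction. The intent is accepted. The table still prints the wrong dose for a 240 subject, and it is where the text sends the site.

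The phrase about the next lower level is also less clear than it looks. In the combination table, the step below −1 (240 with dabrafenib 150) is −2 (240 with dabrafenib 100), which leaves E6201 unchanged. That is correct, and it widens the problem: a subject with a DLT is not certain to have E6201 reduced either.

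The start-dose problem is conditional, the de-escalation probabilities rest on assumed rates, and 18 is the number who could start at 240, not the number who would reach an affected row. All of that stands, and the last number cannot be estimated from the documents. Monthly safety calls (Section 10.3.1.8) and the Safety Review Committee's review before Expansion give chances to notice the error. They do not correct the table, and run-in subjects may be treated under it first.

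Finally, a 320 start is not wholly immune. After a second Grade 2 event takes a subject to 240, a first Grade 3 event prints 240 again. After a Grade 4 event takes a subject to 160, a first Grade 3 event prints 240, a higher dose. These mixed-grade sequences are a reason to write the rule relative to the current dose.

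**Conclusion.** The concern holds, and the table is wrong as written. For a subject assigned 240 mg/m², two of the five dose-change rows give no reduction, against the stated next-lower-level rule and the table's own wording. The excess over the intended dose is 480 mg/m² per full cycle (50%). For a subject assigned 160, two rows print an increase, but that start lies outside the anticipated run-in size.

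The start-dose problem needs E6201 to be de-escalated, for which the probability runs from 11% to 73% over the assumed DLT rates and the two stopping rules. If the MTD is a 240 level, up to 18 subjects counted in Expansion start there. It should be corrected before any subject is treated below 320. The row arithmetic is certain; how many subjects would meet an affected row is unknown.

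**What to change.** Amend Table 4 as follows.

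- In the four Grade 2 and Grade 3 dose-change rows, replace the absolute doses with a reduction of one E6201 dose level from the current dose (320 to 240 to 160 mg/m²). Naming the E6201 level removes the ambiguity with the combination levels.
- For a first Grade 4 event that is not life-threatening, state that treatment resumes at 160 mg/m².
- State that no subject resumes above the current dose.
- For a subject already at 160, refer to the existing rule in Section 5.5.1.2 on stopping E6201 when that dose proves unsuitable. Do not add automatic discontinuation for recurrent Grade 2 events. A 240 starter may therefore stay at 160 after a further event, on judgment, because no lower level exists.
- Leave the permanent-stop rows unchanged (fourth Grade 2, third Grade 3, second Grade 4).
- Limit the 75% and 50% labels to a 320 start, or drop them.

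Table 7 already uses relative wording for most dabrafenib reductions, so this suits the protocol's style.

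The cost is table wording in an amendment, with two effects on dosing. Subjects starting at 240 reach 160 one event sooner than the table now prints: at the second rather than the third Grade 2 event, or the first rather than the second Grade 3 event. A 320 subject already reduced to 240 for a second Grade 2 event goes to 160, not 240, at a first Grade 3 event.
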